 - a. Given these successes and challenges and the potential beneficial effects on mortality described in Section 11.2, a study comparing two interventions to Usual Care that will answer our original research questions prior to study closure will be challenging but remains feasible. Answering the question whether mechanical ventilation or intravenous hypertonic saline decreases mortality risk in children with CM requires sing participants enrolled in the BMP observational study prior to clinical trial commencement as Historical Controls (obviating the need for randomizing high numbers of participants into the Usual Care arm)

Historical Controls:

We identified potential Historical Controls from the electronic database of the completed observational study of cerebral malaria pathogenesis. In order to minimize temporal differences between participants randomized in the clinical trial, we began our search with children enrolled in the observational study in 2017 and moved backwards in time.

Neuroradiologists affiliated with the Treating Brain Swelling clinical trial assessed the brain MRI scans on over 200 children enrolled in the observational study. These images dated from 2014-2017.

Once consensus brain volume scores on these MRI scans were assigned by the neuroradiologists, we retrieved demographic and clinical data on children who had assigned brain volume scores of 6-8 from the master Blantyre Malaria Project database. Demographic, clinical, and outcome data were compared between children enrolled in the observational study who had brain volume scores of 6-8, and children randomized in the Treating Brain Swelling clinical trial and were randomized to Usual Care with the same range of brain volume scores. Comparisons were made between the following variables: age (in months), sex, Blantyre coma score, admission glucose, admission hematocrit, admission platelet count, and outcome. Statistical analysis: Comparisons between groups were made using t-tests or Wilcoxon test (continuous variables), ANOVA (categorical variables), or chi squared tests (dichotomous variables), as appropriate.

We found no difference in the variables in question between children enrolled in the observational study who had MRI brain volume scores of 6-8, and participants randomized in the clinical trial who had MRI brain volume scores of 6-8.

Table 4. Continuous variables compared between historical controls and randomized study participants

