Variable	OS mean	OS SD	TBS mean	TBS SD	P value
Age (months)	48.25	27.54	59.63	27.88	0.168
Glucose	5.87	2.94	5.63	3.13	0.914 ^d
Hematocrit (%)	23.36 ^a	6.29	25.54	6.97	0.555 ^d
Platelets (*1000/MicroL)	148.9 ^b	373.7	94.3 ^c	176.2	0.993 ^d

OS= observational study (n=48), SD= standard deviation, TBS= treating brain swelling clinical trial (n=16)

^a n=45, ^b n=47, ^c n=15. ^d nonparametric test.

There was no significant difference in admission Blantyre Coma score (p=0.948), sex (p=0.885) or outcome (death/survival, p=0.551) between the 48 children in the observational study and the 16 randomized participants in the Treating Brain Swelling clinical trial.

We therefore conclude that participants enrolled in the observational study (n=48) are comparable to participants randomized to Usual Care (n=16) in the Treating Brain Swelling clinical trial.

We anticipate enrollment in the Usual Care arm in the 2023 season (see below) at a reduced ratio compared to the intervention arms.

Possible future declaration of futility of the ventilation arm:

If we combine the mortality risk in Historical Controls and participants already randomized to Usual Care, the mortality risk of the combined historical control group and children randomized to Usual Care is 36%. At the end of the 2021 season, the mortality risk in the VENT arm was 26.3%. (Five of 19 participants randomized to VENT died or were brain dead.) With only these data, the test of the null hypothesis of a null difference in mortality is not significant (p-value 0.818, 2-sided test).

We believe it likely that VENT will, in the future, be declared futile. If so, randomization of participants enrolled in the Treating Brain Swelling clinical trial after the declaration of futility of VENT would be to HPS or UC. A formal approach to futility assessment for VENT is provided below.

Table 4. Projected enrollment

	2018 – 2021	2022	2023	Total
*Usual care (UC)	64	0	4	68
Ventilatory support (VENT)	19	7	6	32
Hypertonic saline (HPS)	3	14	15	32

*historical controls + study participants enrolled in 2018 and 2019.

Assuming that enrollment in 2023 follows the same trend seen since the beginning of the clinical trial, we will be able to detect a 50% or more risk reduction in either the VENT or HPS arms, compared to UC.

Choice of interventions

The three study arms of the study will be:

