5.2 Subject Exclusion Criteria

Subjects showing evidence of the following at baseline will be excluded from the study:

- Gross malnutrition as evidenced by peripheral edema, hair color changes, or severe wasting
- Advanced Human Immunodeficiency Virus (HIV) disease – defined as known HIV positive status and evidence of severe wasting
- Evidence of recent head trauma by history or physical examination

- Evidence of severe co-morbidity at time of initial evaluation
 - Pneumonia as evidenced by oxygen saturation on room air of <85%
 - Gastroenteritis and shock as evidenced by capillary refill >3 seconds or skin tenting

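### The described selection of the 48 historical controls has no step applying the trial's own eligibility criteria, so the fixed usual-care benchmark may include children who could not have been randomised

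*Combined protocol and SAP*

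**What the plan says.** The Historical Controls text in Section 4 describes the route to the 48 controls. On calendar time: "we began our search with children enrolled in the observational study in 2017 and moved backwards in time". On imaging, the trial's neuroradiologists "assessed the brain MRI scans on over 200 children enrolled in the observational study", with images from 2014 to 2017. On the final selection: "we retrieved demographic and clinical data on children who had assigned brain volume scores of 6-8". The source is a completed observational study of cerebral malaria. The text mentions no other filter.

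Trial children pass a further filter. Section 5.1 sets the screening criteria, including age 6 months to 12 years. Section 5.2 opens: "Subjects showing evidence of the following at baseline will be excluded from the study". Its list includes "Gross malnutrition as evidenced by peripheral edema, hair color changes, or severe wasting", advanced HIV disease, recent head trauma, and severe co-morbidity. The last is given as "Pneumonia as evidenced by oxygen saturation on room air of <85" per cent and "Gastroenteritis and shock as evidenced by capillary refill >3 seconds or skin tenting". Section 7.1 repeats the oxygenation and perfusion limits at screening.

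Section 4 compares the 48 with the 16 children randomised to UC on age, sex, Blantyre coma score, glucose, hematocrit, platelets and outcome. It finds no significant difference and concludes: "We therefore conclude that participants enrolled in the observational study" are comparable to the randomised UC children. Section 11.5 pools the two groups into a UC arm of 64. Section 11.6 fixes UC mortality at 0.28 on that basis and tests VENT against it one-sided at 0.05. Section 11.7 makes that test the primary analysis.

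**The concern.** A comparator should consist of children who could have entered the arm it is compared with. As described, the controls were filtered on source study, year and MRI score, while VENT and HPS children were also filtered on hypoxia, perfusion, nutrition, HIV disease and trauma. Section 5.2 itself labels hypoxia and shock as severe co-morbidity, so higher mortality in such children is a reasonable expectation. If they are present only on the control side, the benchmark is raised for a reason unrelated to treatment.

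The design has little to absorb such a bias. Three-quarters of the UC group is historical, the projected enrolment table in Section 4 adds only 4 UC children after 2021, and the VENT test treats the benchmark as known. An error in it passes straight into the primary test. HPS is also compared with this UC group (Section 11.5), so the same direction of bias applies there, although it is not quantified here.

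The comparability check cannot settle the matter because none of its variables is a 5.2 condition.

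**Working it through.** **Inputs from the documents.** UC group 64 = 48 historical + 16 randomised (Section 11.5), so the historical share is 48/64 = 75%. Benchmark p0 = 0.28, target 0.14, one-sided alpha 0.05, power 80%, stated sample 38 (Section 11.6). Projected VENT total 32 (Section 4).

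**Reproducing the plan's figure.** One-sample test with the variance taken at the alternative: n = (1.645 + 0.842)² × 0.14 × 0.86 / 0.14² = 37.98, that is 38. So the stated sample does treat 0.28 as a known constant.

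**Inputs not in the documents (assumptions).** Let k of the 48 be ineligible and let a fraction m of those have died. Take k = 2 to 8 and m = 0.50 to 0.75.

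**Effect on the benchmark.** 28% of 64 is about 18 deaths. The eligible-only rate is (18 − k·m)/(64 − k). The last two columns give the chance of a result at least that good if VENT mortality truly equals this rate. Four of 32 and 5 of 38 are the largest counts significant at 0.05 in a single-look exact binomial test against 0.28 (5/32 gives 8.1% and 6/38 gives 6.2%).

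| k | m | Eligible-only rate | P(≤4 of 32) | P(≤5 of 38) |
|---|---|---|---|---|
| 0 | – | 28% (as stated) | 3.3% | 2.6% |
| 2 | 0.50 | 17/62 = 27.4% | 3.8% | 3.1% |
| 3 | 0.50 | 16.5/61 = 27.0% | 4.2% | 3.4% |
| 5 | 0.50 | 15.5/59 = 26.3% | 5.1% | 4.3% |
| 2 | 0.75 | 16.5/62 = 26.6% | 4.7% | 3.9% |
| 3 | 0.75 | 15.75/61 = 25.8% | 5.7% | 4.8% |
| 5 | 0.75 | 14.25/59 = 24.2% | 8.5% | 7.6% |
| 8 | 0.50 | 14/56 = 25.0% | 7.0% | 6.0% |
| 8 | 0.75 | 12/56 = 21.4% | 15.4% | 14.7% |

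With the k = 5, m = 0.75 rate rounded to 24%, the two tails are 8.8% and 7.9%.

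**Second route.** Let a share f of the 48 be ineligible, with mortality r times that of eligible children. Then the eligible rate is e = 0.28/(1 + 0.75·f·(r − 1)). The single-look normal approximation to the true one-sided error with n = 38 is Φ[(0.28 − e)/√(e(1 − e)/38) − 1.645]. For f = 5%, r = 1.5: e = 0.275, error 5.8%. For f = 20%, r = 2: e = 0.243, error 13.1%. If f = 0 or r = 1, the error stays at the nominal 5%.

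**The other benchmark.** Section 4 and Section 11.5 give UC mortality as 36%, about 23/64. The same formula, (23 − k·m)/(64 − k), gives 35.5% at k = 2, m = 0.50 and 30.4% at k = 8, m = 0.75. The 8-point gap between 36% and 28% exceeds the largest shift in the table (28.1% − 21.4% = 6.7 points). That conflict is a separate matter, but it has to be resolved before any corrected rate can be stated.

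**Reassurance from the comparability test.** With 48 against 16 children, a two-sided 0.05 test has about 20% power to detect mortality of 36% against 20%, and about 28% for 40% against 20%. The reported p = 0.551 for outcome therefore says little.

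**The case against.** A reader might infer that the exclusions were not applied, and that the controls are in fact sicker. The documents support neither statement. Both are inferences from silence: the observational study's entry criteria are not given and may overlap with Sections 5.1 and 5.2 in part or in full. The step from over 200 scans to 48 controls is not itemised. Controls also had to be enrolled in a cerebral malaria study and to have had an MRI, and either condition could have removed some trauma cases or unstable children. The comparisons that Section 4 reports show no difference in coma score (p = 0.948), glucose, hematocrit or death. They are weak, but they do not point to sicker controls.

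The size is also open to challenge. Both k and m are assumed, and at the low end (k = 2, m = 0.50) the tail moves only from 3.3% to 3.8%. Section 11.6 specifies a four-stage power-family design, so 4/32 and 5/38 are not its boundaries and these tails are not its type I error.

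All of this limits the claim to a conditional one. It does not close the gap: the selection rule as written does not require controls to meet the trial's criteria, and nothing in the documents lets a reader verify that they do.

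**Conclusion.** The point stands as a weakness in the stated selection rule, not as a demonstrated bias. The protocol describes no application of 5.1, 5.2 or 7.1 to the historical controls and no comparison on the 5.2 conditions, yet these children make up 75% of a benchmark treated as fixed in a one-sided primary test. If some were ineligible and had higher mortality, the direction is towards benefit for VENT and HPS.

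The size cannot be determined from the documents and may be nil. Under the stated assumptions the 28% benchmark falls to between 27% and 21%. For 2 to 5 ineligible children, the single-look chance of 4 or fewer deaths in 32 under no effect goes from 3.3% to between 3.8% (half of them died) and about 8.8% (three-quarters died). So a handful of records could take a nominal 5% test over its level, or could make almost no difference. That is enough to justify checking them.

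**What to change.** In the Historical Controls text of Section 4, require each of the 48 to meet Section 5.1 and to be free of the exclusions in Sections 5.2 and 7.1. Have this checked from the observational-study database by someone who does not see the outcome, since outcomes are already known. Exclude those who fail, and report how many failed and on which criterion. Recompute the UC rate, the UC sample size, and the power, boundaries and conditional power in Sections 11.5 to 11.7 on the eligible set. Add a sensitivity analysis that omits controls whose status cannot be established. If the observational study already applied the same criteria, say so and cite them; if no control fails, report that.

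The cost is a check of 48 records and the possible loss of a few controls. Some items, such as capillary refill or wasting, may not have been recorded; the documents do not say, and hematocrit and platelets are already incomplete (45 and 47 of 48). If the rate changes, the sequential boundaries must be re-derived after two stages have already been assessed against 0.28, which is more than a change of wording. No randomised child's treatment is affected.

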1. Arm 1: Usual care + immediate mechanical ventilatory support (VENT) for a maximum of 7 days, with ventilator withdrawal once brain volume has decreased (brain volume score ≤ 5) or the patient has improved clinically (modified Blantyre Coma Score ≥ 3) or the patient dies or meets criteria for severe irreversible neurologic failure.
2. Arm 2: Usual care + intravenous hypertonic saline (HPS) for a maximum of 7 days, withdrawn once brain volume has decreased (brain volume score ≤ 5) and the patient

has improved clinically (Blantyre Coma Score ≥ 3) or the patient dies or meets criteria for severe irreversible neurologic failure.

3. Arm 3: Usual care (UC); intravenous fluids, intravenous artesunate; antipyretics, anticonvulsants and blood transfusions as needed; nutritional support) for a maximum of 7 days, or until brain volume has decreased (brain volume score ≤ 5) and the patient has improved clinically (Blantyre Coma Score ≥ 3) or the patient dies or meets criteria for severe irreversible neurologic failures

Participants will remain in the study throughout their hospitalization and, in survivors, through the 12-month post-randomization follow-up visit. Children are discharged when two sequential 6-hourly blood films are free of malaria parasites, when they have been afebrile for 24 consecutive hours, and when they are able to take medications and food by mouth. Final data collection will be at 12 months post-randomization.

Stratification:

No stratification is required. The ages of retinopathy-positive CM with severely increased brain volume per MRI who survived were compared to those of participants from the same population that died. There was no difference in the age structure (data not shown, $p=0.95$).

Primary and secondary outcomes.

The primary outcome is treatment success or failure, determined within the first 7 days. Treatment success is recovery. Treatment failure is death, ventilatory rescue (for participants in Arms 2 and 3) or meeting criteria for severe irreversible neurologic failure.

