5.3 Treatment Assignment Procedures

5.3.1 Randomization Procedures

The study will be randomized, but not blinded. Participants will be randomized after completing the eligibility screening procedures. A block randomization scheme will be used to ensure groups of equal size. Blocks sizes of six and nine will be rotated to decrease the predictability of group allocation within a block for data collectors. Children with retinopathy-positive CM will be randomized separately from those with retinopathy-negative CM.

Randomization is based on obtaining a consensus interpretation of brain volume per MRI. If this is not possible for any reason, study participants will be screened but not randomized, and will remain on the PRW. All other study procedures will be followed as described in this protocol.

Randomization is predicated on the risks and benefits as described in this protocol. Endotracheal intubation is required for participants randomized to the “intubation + mechanical ventilation” arm. The current coronavirus pandemic affects the risk/benefit ratio of this arm of the study because endotracheal intubation increases the risk of aerosol spread of the coronavirus (US CDC COVID19 guidance, 4.4.20, www.cdc.gov/coronavirus/2019-ncov/hcp/guidance-risk-assesment-hcp.html). Randomization to the mechanical ventilation arm will be adjusted in accordance with local IRB recommendations during the coronavirus pandemic.

All possible blocks with balanced combinations of group assignment will be documented. Next computer-generated random numbers will be used to select from the balanced blocks. Assignment of study subjects to randomization arm will be performed electronically, through the online data capture mechanism. If Internet service is unavailable at the time of randomization, back up sequentially numbered opaque sealed envelopes prepared before the trial begins will be available. The envelopes will be stored in a secure location with access limited to key study personnel. After a caregiver provides consent for a patient to participate in the study, study arm assignment will first be attempted electronically. If Internet service is unavailable, study personnel will open the next unopened sequentially numbered envelope to reveal the group assignment and dosing calculation sheet.

A master log of all screened and enrolled subjects will be maintained. A subject is considered randomized upon online assignment or opening the envelope to indicate treatment assignment.

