Transcranial Doppler: TCD examination will be performed at enrollment and every 24 hours thereafter while the patient is hospitalized. Middle cerebral arteries (MCAs), extracranial internal carotid arteries (EC-ICAs), and basilar arteries (BAs) will be insonated at 1 mm intervals using the transtemporal or occipital acoustic windows. Systolic (Vs), diastolic (Vd), mean flow velocities (Vm) and pulsatility index (PI) will be recorded at each interval. Based on findings of TCD examinations, subjects will be placed into phenotypic groups.

Neurological exam: A focused neurological examination will be performed at admission, and at 0800 and 1600 daily (\pm 2 hours) while the patient is comatose (BCS \leq 2). A detailed neurological examination will be performed at each of the 1, 6, and 12 month (\pm 2 weeks) post-randomization follow-up visits. While hospitalized, the examination will focus on candidate neurological exam markers of increased brain volume: restriction or changes in eye movements, abnormal posturing (decerebrate, decorticate), changes in reflexes (corneal, gag, deep tendon). The follow-up neurological history and examinations will focus on determination of hard neurological abnormalities: tone, reflexes, movement, posture, interim unprovoked seizures, Neurological

development will be determined by administration of the Malawi Developmental Assessment Test or Kaufman Assessment Battery for children, depending on the age of the subject at the time of enrollment.

Brain swelling intervention: After brain MRI screening, subjects with severely increased brain volume scores (≥ 6) will be eligible for randomization. The parent/ caregiver will be approached for informed consent using the Randomization Consent document. If consent for randomization is granted, randomization assignment will be determined online or opening the next sequentially numbered sealed randomization envelope (stratified by malarial retinopathy status) and the subject's assignment to each of the three study arms determined.

Subjects may be randomized to:

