11.2 Stratification and Randomization

Stratification by retinopathy status (negative/positive) is necessary as the mortality rates vary between children of varying retinopathy status. For this study, stratification by gender or age is not necessary.

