11.7 Statistical Analysis

For the primary outcome, the test of the null hypothesis $H_0 : \theta = 0$ vs $H_1 : \theta < 0$ for the mortality difference $\theta = p - p_0$ follows from the sequential design described in 11.6. The preferred analytic method for secondary outcomes by type/scale is included in Table 8. The unit of analysis is the individual child (indexed by i) with a single outcome measure Y_i and covariates \mathbf{x}_i which includes an indicator for treatment arm (VENT, HPS, UC), socio-demographic and clinical variables whose prognostic influence on the outcome is of interest or needs to be controlled. The ensuing data on the N children are $\{(Y_i, \mathbf{x}_i) : 1 \leq i \leq N\}$. We expect $N=128$ across all three arms. Depending on whether the early stopping and futility rules are triggered in 11.6, sample size will vary by treatment arm. Minimum size in UC is 64 if no new recruitment into this arm is made in 2022 and 2023. Minimum size in HPS is 32, and in 21 in VENT if futility is triggered. With these caveats we describe broadly our statistical analyses.

Analysis of binary outcomes in Table 8 is by logistic regression. Continuous variables such as optic nerve sheath diameter on admission, heart rate variability patterns, and opening CSF pressure on admission are analyzed using linear models. To mitigate the effects of skewness in their distributions, if found, a logarithmic or square-root transformation g will be applied to Y_i and analysis carried out on the transformed variable. To assess the effect of treatment on outcome we will fit the linear model $E(g(Y_i) | \mathbf{x}_i) = \mathbf{x}_i' \beta$ and test the hypothesis $H_0 : \beta_1 = 0, \beta_2 = 0$ where β_1 and β_2 are the coefficients for the VENT and HPS, respectively. Point estimates and

associated 95% confidence intervals for response mean on the original scale will be calculated and would involve smearing.²⁶⁰⁻²⁶²

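### Randomisation is stratified by retinopathy, but Section 4 says no stratification is needed, and the primary test against largely historical controls has no committed retinopathy adjustment

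*Combined protocol and SAP*

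**What the plan says.** Four places in the protocol treat retinopathy as a stratification factor.

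- Section 11.2: "Stratification by retinopathy status (negative/positive) is necessary as the mortality rates vary between children of varying retinopathy status". The same section adds "For this study, stratification by gender or age is not necessary".
- Section 5.3.1: "Children with retinopathy-positive CM will be randomized separately from those with retinopathy-negative CM".
- Section 8.1 describes the back-up envelopes as "stratified by malarial retinopathy status".
- Section 2.3 says the two retinopathy groups are randomised independently of each other.

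Section 4, under its Stratification heading, says "No stratification is required". Its only support is an age comparison between survivors and deaths among retinopathy-positive children: "There was no difference in the age structure" (p=0.95).

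On analysis, Section 11.7 says that the primary test "follows from the sequential design described in 11.6". Section 11.6 defines a four-stage, one-sample test of ventilation-arm (VENT) mortality p against a fixed p0 = 0.28. Table 8 lists logistic regression for the primary outcome without naming a retinopathy term.

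Retinopathy appears in two other analysis provisions. Section 2.1.13 plans a sensitivity analysis of whether treatment effects differ by retinopathy status. Section 11.3 includes retinopathy among the baseline variables to be compared across arms and permits regression adjustment where differences are substantive.

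Section 4 compares the historical controls with randomised usual-care children on age, sex, coma score, glucose, hematocrit, platelets and outcome. Retinopathy is not on that list.

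**The concern.** The protocol judges retinopathy prognostic enough to randomise by, then leaves it out of the test that decides the trial. In an ordinary concurrent trial the cost would be mainly some precision, because stratified allocation balances the factor. Here that protection does not reach most of the comparison. Section 11.5 builds the usual-care group from 16 randomised children and 48 children from the 2014-2017 observational study. Stratified allocation cannot balance retinopathy between randomised children and children who were never randomised.

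If the retinopathy mix differs between VENT and the group that supplied p0, the difference in mortality caused by mix is counted as treatment effect. The historical-control comparison would be the place to detect this, but it omits the factor. The unqualified sentence in Section 4 adds a second problem: a reader who relies on it would conclude that retinopathy plays no part in the design.

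**Working it through.** **1. Reproduce the plan's figure.** Section 11.6 gives p0 = 0.28, a 50% relative reduction (p1 = 0.14), 80% power and a lower-tailed alpha of 0.05, and states 38 subjects. The one-sample normal approximation with variance at the alternative gives

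n = (1.645 + 0.842)² × 0.14 × 0.86 / (0.28 − 0.14)² = 37.98, so 38.

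The figure reproduces from a formula with one pooled p0. No stratum information enters.

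**2. Bias from a difference in mix.** Let f_V and f_C be the retinopathy-positive shares in VENT and in the children behind p0. Let mortality be 0.37 in positives (Section 4) and q in negatives. With no treatment effect, the expected contrast is

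(f_V − f_C) × (0.37 − q).

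The documents do not give q for severe swelling, so it is an assumption. Absolute shifts, in percentage points:

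| q (assumed) | 10-point mix difference | 20-point mix difference |
|---|---|---|
| 0.10 | 2.7 | 5.4 |
| 0.20 | 1.7 | 3.4 |
| 0.30 | 0.7 | 1.4 |
| 0.37 | 0 | 0 |

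The target difference is 14 points. The sign follows f_V − f_C: with q below 0.37, fewer positives in VENT flatters ventilation and more positives works against it.

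**3. Is a 10-point mix difference plausible?** Section 4 expected 30-35 positive and 10-12 negative children a year, that is 30/42 = 71% to 35/45 = 78% positive. Take 75%, with 32 VENT children (projected enrolment table, Section 4) and 64 usual-care children (Section 11.5):

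SE = √[0.75 × 0.25 × (1/32 + 1/64)] = 0.094.

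A gap of at least 10 points in either direction would arise by sampling alone about 29% of the time (z = 0.10/0.094 = 1.07). Any change in mix over calendar time would be additional. The actual mixes are not reported.

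**4. Effect on the error rate (illustration only).** A single-stage exact rule with n = 38 and p0 = 0.28 rejects at 5 or fewer deaths. Its rejection probability under no treatment effect depends on the VENT mortality that the mix implies:

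| No-effect VENT mortality | Rejection probability |
|---|---|
| 0.226 (shift of −5.4 points) | 0.11 |
| 0.24 | 0.079 |
| 0.28 | 0.026 |
| 0.32 | 0.007 |

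These are not the error rates of the four-stage boundary. They show only that the operating characteristics depend on a mix that the test does not use.

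**5. Do the other provisions close the gap?** The Section 2.1.13 analysis asks whether the effect varies by retinopathy, which is a different question from adjusting the overall contrast. Section 11.3 says only that adjustment may be made, after the data are seen, and it concerns the study arms. Table 8 supplies a suitable model but does not specify the covariate.

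**The case against.** **The Section 4 sentence is probably a slip.** Its only support concerns age. Read as referring to age, it agrees with Section 11.2. A reader might infer that allocation was unstratified or is in doubt. The documents do not support that, since Sections 2.3, 5.3.1, 8.1 and 11.2 all stratify by retinopathy. This objection stands, so that part is a wording correction.

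**The plan does use retinopathy.** A reader might infer that it is ignored throughout. It is not: Sections 2.1.13 and 11.3 both name it, and the models in Section 11.7 allow clinical covariates. What remains is that none of these commits to adjusting the primary contrast.

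**The size is assumed.** No retinopathy-negative mortality is given for severe swelling, and no mix is given for VENT or the historical controls. Section 2.1.10 says imaging predictors of death in retinopathy-negative children are unclear. Section 11.2 says mortality differs but not by how much. This stands. The bias could be negligible and its direction is unknown.

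**Replacing the test is not free.** A reader might infer that the one-sample test should simply become a stratified two-sample test. Two stages have already been analysed, and the boundaries belong to the one-sample design. An unstratified, fixed-sample check for 38 against 64 children at 14% versus 28%, one-sided 0.05, gives SE = √(0.14 × 0.86/38 + 0.28 × 0.72/64) = 0.0795 and power Φ(0.14/0.0795 − 1.645) ≈ 55%. With a pooled null variance it is about 49%. The stated figure is 80%. This stands, and the fix below therefore leaves the test alone.

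**Historical controls raise a wider problem.** One covariate would not remove their other differences. That is true, but it is no reason to omit the factor that the protocol itself names as prognostic.

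**Conclusion.** The concern holds in limited form. Section 4 conflicts as written with the rest of the protocol. The primary test has no retinopathy term, and no other provision commits to adjusting the primary contrast for it. The omission matters mainly because three-quarters of the usual-care group (48 of 64) is historical and was not compared on retinopathy.

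The possible shift is about 0.7 to 5.4 points in either direction, against a 14-point target. That range assumes 10% to 30% mortality in retinopathy-negative children and a mix difference of 10 to 20 points. It also carries over the 37% for severely increased volume to a trial that now admits brain volume scores from 6. The shift is zero if mortality or mix is equal. A reader might infer that the trial is biased towards ventilation by several points; without the missing mortality and mix, the documents show only that such a bias is possible and would go uncorrected.

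**What to change.** 1. **Section 4.** State that no stratification by age or gender is needed and that randomisation is stratified by retinopathy status, in line with Sections 2.3, 5.3.1, 8.1 and 11.2.
2. **Table 8 and Section 11.7.** Name retinopathy status as a fixed covariate in the logistic regression for the primary outcome, for VENT versus usual care and for hypertonic saline versus usual care. Report the adjusted estimates alongside the sequential test and leave the existing boundaries in place.
3. **Historical controls (Section 4).** First confirm that retinopathy was recorded for these 48 children, because the documents do not say so. If it was, add it to the comparability table and report the mix for historical controls, randomised usual care, VENT and hypertonic saline. If it was not, state this as a limitation; adjusted estimates that include those children would then not be available without further assumptions.

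The cost is a little more analysis, one extra model parameter in a small sample, and possibly some record retrieval. If the sponsor prefers to replace the one-sample test with a stratified two-sample test, the boundaries and power must be recomputed, and the stated 80% should not be carried over.
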